5.4.2. Transitioning to Study VKA at Randomization

For subjects randomized to VKA who require switching from another anticoagulant (another VKA, other non-VKA OAC drugs or parenteral anticoagulants), follow the guidance for switching in the locally approved labels of these products. Capture the date and timing of first study dose in eCRF.

Table 5.4: Transitioning to Study VKA at Randomization

Switching to VKA		
From	To	Recommendation
Vitamin K Antagonist (VKA)	Study VKA	If the INR measured on the day of randomization is: 
 ≤ 2.5, start study VKA > 2.5, the Investigator or designee must recheck at a later time; start study VKA when the INR is ≤ 2.5; document the INR value and the date it was measured.
Other non-VKA OAC drugs 
 dabigatran rivaroxaban apixaban 	Study VKA	Ascertain adequate anticoagulation until an INR ≥ 2.0 is reached and then continue with study VKA only. Follow local label of country-selected VKA and label of NOAC being stopped for further guidance.
Parenteral anticoagulants	Study VKA	For subjects not previously on VKA, bridging with parenteral anticoagulation is permissible, but not recommended. For initiation of VKA therapy and related bridging with parenteral anticoagulation, follow locally established guidelines and local approved label (prescribing information) from the VKA manufacturer.

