5.4.3. INR Management

Every effort should be made to optimize the VKA dosing and INR monitoring schedule to maintain INR values between 2.0-3.0 inclusive.

INR management is according to the standard of care and may be performed by the Investigator, the subject's primary care physician or other private physician, at

a specialized anticoagulation clinic or patient self-monitoring. Close attention to the INR management plan and frequent monitoring of INR values is strongly recommended to optimize the VKA treatment and maintain the subject's INR values between 2.0-3.0 inclusive. The Investigator will ensure the VKA is used according to the approved label (prescribing information).

Daily INR determinations upon initiation should be obtained until subject's INR is stable in the therapeutic range. It may take 4-14 days to attain the target - - therapeutic range of INR 2'.. 2.0.

Obtain subsequent INR determinations as per recommendations and guidelines provided in the local approved label from the respective VKA manufacturer.

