- The assigned treatment regimen and the proper daily dosing is explained to the subject including confirmation that the subject understands the proper daily dosing;
- Collection of a 12-lead ECG recording (see section 9.8). The last post-index PCI ECG recorded before randomization can be used;
- Collection of the re- and Rost-angiograms for the index=PCI (see section 10.1);
- For subjects randomized to the edoxaban-based regimen:
 - Administer the first dose of edoxaban and of study P2Y12 inhibitor according to Section 5.3.2 and 5.5.2, respectively.
- For subjects randomized to the VKA-based regimen:
 - Administer the first dose of VKA, of study P2Y12 inhibitor and of ASA according to Section 5.4.2, 5.5.2 and 5.6.2.

At hospital discharge or at the outpatient clinic:

- Dispensation of assigned study medication and of the medication log to the subject; Medication may be distributed to patients in an unbranded bag for convenience.
- Instruction is provided to the subject to bring all study medications including anticoagulant and antiplatelet medications to each visit as well as the filled in medication log;
- Schedule the next on-site visit through the IXRS (i.e. Visit 2 at 1 Month).

Information to be recorded in the eCRF:

- The following information is recorded in the eCRF:
 - o The date and timing of the first dose of each study medication
 - o All determined INR values and dose adjustments to reach target INR range of 2.0- 3.0 inclusive;
 - o Significant physical findings under medical history;
 - o Medical history including components of the CHA2DS2-VASc score, HAS-BLED score (Appendix 17.5) and past history of bleeding events;
 - o All medications the subject was taking within 30 days prior to randomization (including medications given before and during the PCI procedure) see section 5.10;
 - o Obtain a copy of the PCI procedure report and record information about index-procedure (e.g. but not limited to vascular access, lesions treated, stents used, procedure result);

- o Local laboratory cardiac enzymes *before* and *after* index-PCI, if available (the closest to the index-PCI procedure and the most recent prior to randomization, respectively).
Consider collecting (it is not necessary to wait for these test results before randomizing the subject):
 - Cardiac troponin (cTn)
 - Creatine phosphokinase MB isoform (CK-MB)
- o Last local laboratory test results, done post-index PCI:
 - Hemoglobin (Hgb)
 - Platelet count

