Abbreviations: AE = adverse event; ALT= alanine transaminase; AST= aspartate transaminase; ALP= alkaline phosphatase; CrCL = creatinine clearance; estimated glomerular filtration rate (GFR) M = month; ECG = electrocardiogram; eCRF = electronic case report form; EOT = end- of- treatment; h = hours; ID = identification; INR = international normalized ratio; IXRS = Interactive WebVoice Response System; LD = last dose; OAC = oral anticoagulant; P C I = percutaneous coronary interver tion; TA= Telephone assessment; TBL = total bilirubin; VKA = Vitamin K antagonist; V = On-site visit; WBC = white blood cell.

• Visit/assessments windows are provided as a guide, but visits should be scheduled taking into account the need to dispense study medications.

^b INR must be 5 2.5 at screening.

- o Check the most recent results from local laboratory tests done post-index PCI against the exclusion criteria (estimated CrCL, hemoglobin, platelet count and WBC with differential if elevated). CrCL should be calculated by the Cockcroft-Gault formula as described in Appendix 17.6.
- d S subjects eligible to participate in the study provide Written IC before randomization or any study-specific procedures. Once written IC is obtained, subject should be randomized without delay.
- o Pre-declaration of duration of ASA treatment if randomized to VKA and of P2Y12 antagonist other than clopidogrel, if applicable.
- r For subjects randomized to edoxaban: If subject is on: (a) VKA, the first dose of edoxaban can be started when INR \leq 2.5. (b) NOAC, discontinue OAC and start edoxaban at the time of the next scheduled NOAC dose.
Continue clopidogrel bisulfate 75 mg once-daily (or other P2Y12 antagonist) with medication as provided by IXRS and discontinue ASA, if being taken.
For subjects randomized to VKA: If subject is on: (a) VKA, continue with medication as provided by IXRS when INR \leq 2.5. (b) NOAC, discontinue the NOAC and start VKA at the time of the next scheduled NOAC dose.
Continue clopidogrel bisulfate 75 mg once-daily (or other P2Y12 antagonist) with medication as provided by IXRS.
Start or continue ASA (100 mg once-daily), guided by the clinical presentation (ACS or stable coronary disease) and upon the CHA2DS₂-VASc and HAS-BLED score and pre-declare use and treatment duration.

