- o VKA subjects only; INR values and VKA dose are collected monthly and entered into the eCRF either during the on-site visits by local laboratory determination or during the subject's telephone assessments. INR values and VKA doses collected through the general practitioner or local anticoagulation clinic must also be considered and collected but this does not constitute a waiver for subjects planned TA or INR determination during on-site visits.
- p Subjects are transitioned to an available marketed OAC of the Investigator's choice. The Investigator will follow the transition strategy in the applicable product label. Subjects who prematurely discontinue study OAC are requested to continue clinical follow-up with either study visits or telephone contacts according to this schedule.

q All randomized subjects who are on study medication (study edoxaban or VKA) at 365 days, will have a post-treatment contact at 30-37 days after the EQT visit to collect data on concomitant medications, SAEs, and other safe events of interest.

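### For a NOAC-treated subject randomized to VKA, the Schedule of Events footnote omits the anticoagulant cover until INR 2.0 that Table 5.4 calls for

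*Combined protocol and SAP*

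**What the plan says.** Two places in the protocol tell the site how to move a subject from a NOAC to study VKA at randomization.

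- **Section 17.9, Schedule of Events, footnote on starting study drug (VKA arm):** "NOAC, discontinue the NOAC and start VKA at the time of the next scheduled NOAC dose". The line ends there.
- **Section 5.4.2, Table 5.4, row for other non-VKA oral anticoagulants:** "Ascertain adequate anticoagulation until an INR ≥ 2.0 is reached and then continue with study VKA only". The same row adds: "Follow local label of country-selected VKA and label of NOAC being stopped for further guidance".

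Three other places bear on which text governs and how long the switch takes.

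- **Section 6.1.2, Day 1 procedures (VKA arm):** "Administer the first dose of VKA, of study P2Y12 inhibitor and of ASA according to Section 5.4.2, 5.5.2 and 5.6.2".
- **Section 5.4.3, INR Management:** "It may take 4-14 days to attain the target" range, meaning an INR of at least 2.0. Monitoring in that time is close: "Daily INR determinations upon initiation should be obtained until" the value is stable in range.
- **Sections 5.4.1 and 5.4.3:** the Investigator is to see that VKA is used as its label directs.

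**The concern.** The footnote and Table 5.4 address the same patients and the same switch, but only Table 5.4 says what protects the patient while VKA takes effect. Read alone, the footnote describes a straight swap at the next dose time. That would do for a replacement drug that acts quickly. By the protocol's own account, VKA does not.

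What is at stake is the safety of control-arm patients. All subjects have AF with an indication for oral anticoagulation and have just been stented. The Schedule of Events is a summary that site staff may well use during a visit, and nothing in this line tells them that a fuller rule exists elsewhere.

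**Working it through.** The protocol gives no figure to reproduce here. The check is a comparison of texts, with one small piece of arithmetic on timing.

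**1. The two instructions side by side**

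| Element of the NOAC-to-VKA switch | Section 17.9 footnote | Table 5.4 |
|---|---|---|
| When to start VKA | At the next NOAC dose time | Not timed in the row; labels to be followed |
| Cover while the INR rises | Not mentioned | To be ascertained |
| INR at which VKA stands alone | None | At least 2.0 |
| Pointer to label or section | None | Labels of both drugs |

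**2. The footnote against its own neighbours.** Its edoxaban-arm line is almost identical: "NOAC, discontinue OAC and start edoxaban at the time of the next scheduled NOAC dose". For edoxaban this agrees with Table 5.2, and Section 1.1.1.5 describes a rapid onset of action. The VKA-arm line applies the same rule to a drug with a slow onset. For subjects already on a VKA, the same footnote does state an INR condition (2.5 or below). A reader could therefore take the NOAC line, which has none, to be complete. The end-of-treatment footnote of the same table deals with a different transition, but it does refer to the label: "The Investigator will follow the transition strategy in the applicable product label".

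**3. The protocol's standard for the same kind of switch.** Section 5.3.3 (edoxaban to VKA) asks for unbroken, adequate anticoagulation. It offers two ways to achieve it: reduced-dose edoxaban alongside VKA until the INR is 2.0, or a parenteral anticoagulant with VKA. Table 5.4 is in line with that standard. The footnote does not mention it.

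**4. Length and timing of the possible gap.** The inputs are 4 to 14 days to reach INR 2.0 (Section 5.4.3) and randomization from 4 hours to 5 days after PCI (Section 3.1). With a first VKA dose on the day of randomization, and without adding the wait for the next NOAC dose time:

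- earliest: 4 h / 24 + 4 d = 0.17 + 4 = about 4.2 days after PCI;
- latest: 5 d + 14 d = 19 days after PCI.

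Fourteen days is not a firm ceiling. Section 5.3.3 expects 85% of patients to reach INR 2.0 by day 14 when edoxaban and VKA are given together.

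**5. Which text governs.** I found no rule of precedence between the body and the appendix table. The Day 1 procedure names Section 5.4.2 for the first VKA dose, however, so a site that follows the visit procedures arrives at Table 5.4.

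**The case against.** The strongest reply is that this is an omission in an appendix footnote, already covered where the dose is actually given. Section 6.1.2 points to Section 5.4.2. Section 5.4.2 opens by sending the site to the local labels for switching, and Table 5.4 repeats this. Sections 5.4.1 and 5.4.3 require use according to the label. Randomization takes place before discharge, the first dose is supervised (Section 5.8), and frequent INR checks would show a value below 2.0. All of this stands, and it makes harm unlikely at a site that follows the body of the protocol.

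It is also fair to say that the texts can be reconciled. The footnote does not forbid cover. A site that stops the NOAC, starts VKA and bridges parenterally would satisfy both, since Section 5.10.1 exempts such a bridge. The Table 5.4 column is headed as a recommendation, so it directs rather than strictly requires. A direct clash arises only if Table 5.4 is met by continuing the NOAC.

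Two stronger readings are tempting and should be resisted.

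- **That the protocol prescribes an anticoagulation gap, or leaves patients without any anticoagulant.** The footnote is silent on cover, and the INR is rising in the interval, so the exposure is subtherapeutic rather than absent. For that reason the remark in Section 1.3 about antiplatelet therapy given without an oral anticoagulant does not describe these patients.
- **That the treatment comparison is distorted.** Events are counted from randomization in the ITT analysis, so a reader might infer a shift in control-arm event rates. The documents give neither the number of NOAC-treated subjects nor how often a site would use the footnote alone, so no such effect can be derived.

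The reply does not remove the mismatch. The footnote is a current operating instruction, it lacks the one element that protects the patient, and it does not say where to find it.

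**Conclusion.** The inconsistency is real and is a minor-to-moderate safety matter. For the NOAC-to-VKA switch, the Schedule of Events footnote leaves out the cover and the INR threshold that Table 5.4 sets. Table 5.4 is sound and is the operative rule.

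The consequence is conditional. If a site acted on the footnote alone, a patient with AF could be below the therapeutic range for the time VKA takes to act, within roughly the first three weeks after PCI. This rests on the protocol's own 4 to 14 days, on a first VKA dose on the day of randomization, and on no cover being given. No count of subjects and no effect on any endpoint is claimed. That the VKA line was carried over from the edoxaban line is a plausible explanation, but it is only an inference about drafting and the finding does not depend on it.

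**What to change.** Change one line of the footnote in Section 17.9. For a subject on a NOAC who is randomized to VKA, either state the Table 5.4 rule (keep anticoagulation adequate until the INR is at least 2.0, then study VKA alone, following the labels of both drugs) or replace the instruction with a reference to Section 5.4.2. The edoxaban-arm line can stay as it is. Send sites a short letter saying that Table 5.4 applies.

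The cost is one line of text and the letter. Sample size, endpoints and analysis are untouched.
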